#### ***Analysis of all treatment emergent SAEs***

- All serious TEAEs by primary SOC and PT
- All serious TEAEs related to IMP by primary SOC and PT

#### ***Analysis of all TEAEs leading to permanent treatment discontinuation***

- All TEAEs leading to permanent treatment discontinuation by primary SOC, HLGT, HLT, and PT
- All TEAEs leading to permanent treatment discontinuation by primary SOC and PT

#### ***Analysis of on-study AEs***

- All the analyses in above categories, including AEs, SAEs, AEs leading to permanent treatment discontinuation, and AEs leading to death will be summarized for the on-study period by SOC and PT.

#### ***Analyses of events of special interest and events requiring specific monitoring***

Unless otherwise specified, AESI and AERSM will be summarized during the TEAE period by prespecified- grouping (AE category of interest) and PT, showing the number (%) of participants, sorted by decreasing frequency of PT.

#### **Severe hypoglycemia**

The severe hypoglycemia will be analyzed on TEAE period.

The following analysis will be provided for severe hypoglycemia:

- Number (%) of patients with at least one severe hypoglycemia
- Number of events per 100 patient-years of total IMP exposure.

### Pancreatic events

The Pancreatic events will be reviewed, assessed and/or adjudicated by CEC.

The following analysis will be provided for positively adjudicated events during the TEAE period:

- The number (%) of patients with at least one positively adjudicated pancreatitis by type: 1) acute pancreatitis, 2) acute on chronic pancreatitis, 3) chronic pancreatitis, 4) unknown pancreatitis;
- The number (%) of patients with at least one positively adjudicated pancreatic neoplasm by type: 1) malignant - confirmed, 2) Malignant - probable, 3) Benign.

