Every effort should be made to maintain patients in the study. Participants will be followed-up according to the study procedures specified in this protocol up to the scheduled date of study completion, or up to recovery or stabilization of any AE to be followed-up as specified in this protocol, whichever comes last.

If possible, and after the permanent discontinuation of intervention, the participant will undergo a pEOT Visit as soon as possible. Participants will then continue in the study with all study procedures/visits except those associated with IMP administration. Patients will continue to be followed after a CV or renal endpoint occurs irrespective of their treatment status. If the patient does not agree to site visits, he/she will be contacted by telephone to inquire about safety status (including hospitalizations and endpoints). See the SoA ([Section 1.3](#)) for data to be collected at the time of intervention discontinuation and follow-up and for any further evaluations that need to be completed.

As all data until the scheduled date of study completion will be used in statistical analyses, it is important to collect data for all participants, under treatment or not, during the whole duration of the study. A high rate of missing data could jeopardize efficacy results of the study. The Investigators should discuss with the participant key visits to attend. The value of critical study data collected during the participant's continued involvement will be emphasized as important to the public health value of the study. Site personnel will receive training regarding strategies for patient retention, and access to tools to assist with this during the study.

Participants who withdraw from the study intervention should be explicitly asked about the contribution of possible AEs to their decision, and any AE information elicited must be documented.

All cases of permanent intervention discontinuation must be recorded by the Investigator in the appropriate pages of the e-CRF when considered as confirmed.

If after permanent treatment discontinuation, a participant who has discontinued from treatment has reconsidered the decision to permanently discontinue treatment and wishes to later resume IMP, and if the Investigator has determined there is no safety reason prohibiting the patient from

resuming IMP and the selection criteria for the study are still met, the participant may resume IMP with Sponsor approval.

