#### ***Observation period***

The observation period will be divided into 3 periods:

- The pre-treatment period or screening period is defined as the time from signed informed consent up to the time of first injection of the double-blind IMP
- The treatment-emergent adverse event period (on-treatment period) is defined as the time from the first injection of the IMP to the last injection of the IMP + 30 days (or +7 days for hypoglycemia).
- The posttreatment period is defined as the period after the end of the treatment-emergent adverse event period.

The on-study observation period/on-study is defined as the time from first IMP until the end of (the) study date (defined as the last scheduled visit for those who completed the study and the study discontinuation date collected on eCRF form 'Completion of End of Study' for those who did not complete the study. If death is reason collected on the 'Completion of End of Study' form, date of death will be used).

The post-study observation is defined as anything after the on-study observation period.

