#### 2.1.4.1 Adverse events variables

##### *Adverse event classification*

The AE observations will be classified per the observation periods of safety data as defined above into:

- **Pre-treatment AEs** are adverse events that developed or worsened or became serious during the pre-treatment period
- **Treatment-emergent AEs (TEAEs)** are adverse events that developed or worsened or became serious during the on-treatment period
- **Post-treatment AEs** are adverse events that developed or worsened or became serious during the post-treatment period
- **On-study AEs** are adverse events that developed or worsened or became serious during the on-study period

All AEs (including SAEs), AEs of special interest (AESI) and AEs requiring specific monitoring (AERSM) will be coded to a lower-level term (LLT), preferred term (PT), high-level term (HLT), high-level group term (HLGT), and associated primary system organ class (SOC) using the version of MedDRA currently in effect at Sanofi at the time of database lock.

AESI include the following terms:

- Pregnancy of a female participant entered in a study as well as pregnancy occurring in a female partner of a male participant entered in a study with IMP
- Symptomatic overdose (serious or nonserious) with IMP
- alanine aminotransferase (ALT)  $\geq 3$  upper limit normal (ULN) (if baseline ALT <ULN) Or ALT  $\geq 2$  times the baseline value (if baseline ALT  $\geq$ ULN)

AERSM include the following terms:

- Severe gastrointestinal (GI) events
- Severe hypoglycemia
- Pancreatic events (including abnormal values of pancreatic enzymes, pancreatitis and pancreatic neoplasm)
- Calcitonin increase  $>5.9$  pmol/L (20 pg/mL) and thyroid C-cell neoplasm
- Acute renal failure
- Diabetic retinopathy complications
- Severe injection site reaction
- Severe allergic reactions
- Severe immune complex disease

The CEC will review pancreatic events in a blinded manner.

The criteria of AESI and AERSM are defined in below [Table 2](#).

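### The dedicated summaries of pancreatic and thyroid C-cell neoplasms stop 30 days after the last dose and have no on-study version

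*SAP*

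**What the plan says.** SAP 2.3.5.1 limits the adjudicated pancreatic tables in one sentence: "The following analysis will be provided for positively adjudicated events during the TEAE period". One of those tables is "The number (%) of patients with at least one positively adjudicated pancreatic neoplasm by type", the types being malignant confirmed, malignant probable and benign.

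The rule for the wider class is in the same section: "Unless otherwise specified, AESI and AERSM will be summarized during the TEAE period by prespecified- grouping (AE category of interest) and PT". The AERSM list in SAP 2.1.4.1 includes "Calcitonin increase $>5.9$ pmol/L (20 pg/mL) and thyroid C-cell neoplasm". SAP Table 2 identifies the thyroid part through a medullary thyroid cancer CMQ. No exception to the TEAE limit is made for neoplasms.

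SAP 2.1.4 defines the TEAE period as "the time from the first injection of the IMP to the last injection of the IMP + 30 days". The same section defines an on-study period, from first IMP to the end of study date.

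After permanent discontinuation, Protocol 7.1.1 says: "Participants will then continue in the study with all study procedures/visits except those associated with IMP administration". Protocol 4.1 follows every randomized participant to close-out or death, and Protocol 8.3.1 collects AEs and SAEs until the follow-up visit.

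**The concern.** A window of last dose plus 30 days suits acute events. It suits neoplasms poorly, because work-up and diagnosis can come well after the drug was stopped.

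The protocol's own rules can close the window first. Under Protocol 7.1.1 and Appendix 6, a calcitonin value of 50 pg/mL or more leads to permanent discontinuation and specialist referral, and confirmed pancreatitis generally leads to permanent discontinuation. If the neoplasm then found has a recorded onset more than 30 days after the last injection, it is outside the dedicated table.

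The programme has reason to want a full count. Protocol 2.3 reports one medullary thyroid cancer and one pancreatic cancer in Phases 1 and 2, judged by the investigators unrelated and unlikely related respectively. For events this rare, a few cases inside or outside a table can change how it reads.

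**Working it through.** **Which outputs count a neoplasm with onset more than 30 days after the last dose?** The plan gives no figure on this point, so the first check sets the planned safety outputs side by side.

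| Output (SAP section) | Window | Late case included? |
|---|---|---|
| Adjudicated pancreatic neoplasm by type (2.3.5.1) | TEAE | No |
| AERSM grouping, including thyroid C-cell (2.3.5.1) | TEAE | No |
| On-study AEs and SAEs by SOC and PT (2.3.5.1) | First IMP to end of study | Yes, by PT |
| Post-treatment AEs and SAEs by SOC and PT (2.3.5.1) | After the TEAE period | Yes, by PT (SAE table if serious) |
| Listings of pancreatic events and of all adjudicated AEs with outcome (2.3.5.1) | No TEAE limit stated | Yes, for pancreatic events |
| Deaths by period and adjudicated cause (2.3.5.2) | Includes on-study | Only if fatal |

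The on-study paragraph does not extend the first two rows. It applies to the analyses listed above it, by SOC and PT, and the AERSM and pancreatic paragraphs come after it.

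**How much follow-up lies outside the window?** From the documents: about 4000 participants and follow-up of 24 to 36 months (SAP 1.3), so roughly 4000 × 2.5 = 10,000 patient-years. Not in the documents: the IMP discontinuation rate. The 2% per year in SAP 1.3 is study discontinuation. The annual stop probability *a* is therefore assumed.

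With permanent stops at constant hazard λ = −ln(1 − a), follow-up T, and u = T − 30/365.25, the expected time beyond last dose + 30 days is

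u − (1 − e^(−λu))/λ.

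Example, a = 10% and T = 2.5 years: λ = 0.1054, u = 2.418, expected time = 2.418 − 0.2249/0.1054 = 0.283 years, and 0.283/2.5 = 11.3%. Averaging over T uniform on 2 to 3 years gives 11.5%.

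| Assumed IMP stop rate per year | Share of person-time outside window | Patient-years of about 10,000 |
|---|---|---|
| 3% | 3.5% | 350 |
| 5% | 5.8% | 580 |
| 10% | 11.5% | 1150 |
| 15% | 16.9% | 1690 |
| 20% | 22.2% | 2220 |

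Deaths, study dropout, and the days between day 30 and the 6-week follow-up visit for those still on IMP at close-out are ignored. A simulation with 2% per year leaving the study and IMP stop rates of 6% and 9% per year agrees: 659 and 958 of about 9,750 patient-years, or 6.8% and 9.8%.

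These are shares of person-time pooled over arms. They are not numbers of missed neoplasms, and they say nothing about a difference between arms.

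**The case against.** The strongest reply is that nothing is hidden. Late cases are counted by arm in the on-study and post-treatment tables, malignant cancers will usually also enter the SAE tables, and adjudicated pancreatic events are listed with treatment, onset date and outcome. If such events are few, a reader can count them by arm and type from the listing. Safety is descriptive, and both documents put the primary focus of AE reporting on TEAEs.

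Most of this stands, and it rules out several stronger readings that a reader might infer:

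- *Late cancers disappear from the safety tables.* The on-study and post-treatment tables contradict this.
- *The window biases the comparison towards no signal.* Protocol 2.3 says discontinuations appeared dose dependent and gives GI discontinuation of 2.2%, 8.3% and 9.8% on efpeglenatide in three Phase 2 studies, but no placebo figures. More stopping on active drug is plausible. A directional bias in neoplasm counts is not shown.
- *Thyroid C-cell neoplasms are adjudicated.* The SAP names only pancreatic events among the AERSM for CEC review. Protocol 10.1.4.3 leaves other selected AEs to a charter that is not in the documents.
- *The on-study count should be the main table.* That would run against the stated TEAE focus and is a preference.

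The reply does not fully close the gap. SOC/PT tables rest on investigator-reported terms, can spread cases over several preferred terms, and show neither the confirmed/probable/benign split nor the CMQ grouping. A listing is not a by-arm summary, and a count assembled from it after unblinding is not prespecified.

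**Conclusion.** The point holds in a limited form. Two dedicated summaries, adjudicated pancreatic neoplasms by type and the CMQ-defined thyroid C-cell grouping, stop at last injection + 30 days and have no on-study counterpart, although the follow-up and AE collection to support one are planned. The loss is a prespecified by-arm count over full follow-up, not the cases themselves.

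The affected share of person-time rests on an assumed stop rate and a constant-hazard model with permanent stops. An interruption followed by restart stays inside the window, because the window runs to the last injection. No expected number of neoplasms can be derived from the documents. Sample size, power and the primary analysis are untouched.

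**What to change.** In SAP 2.3.5.1, add an on-study count (first dose to end of study date, using the definition in SAP 2.1.4) beside the TEAE count for CEC-adjudicated pancreatic neoplasms by type and for CMQ-defined thyroid C-cell neoplasms. State that TEAEs remain the primary AE focus, and leave acute events, such as pancreatitis, severe GI events and severe hypoglycemia, on their present windows.

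The cost is one extra column in two tables, with no new data collection. The added column will include some cases remote from exposure; keeping the TEAE count next to it lets the reader see which cases those are.

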### ***Analysis of pretreatment and posttreatment adverse events***

- All pretreatment AEs by primary SOC and PT, showing the number (%) of patients with at least 1 pretreatment adverse event
- All posttreatment AEs by primary SOC and PT, showing the number (%) of patients with at least 1 posttreatment adverse event
- All posttreatment SAEs by primary SOC and PT, showing the number (%) of patients with at least 1 posttreatment serious adverse event

### ***Listing***

Supporting AE listings will be provided for SAEs, AESIs, deaths, severe hypoglycemia, pancreatic events and AEs leading to treatment discontinuation and/or death.

These listing sorted by treatment, participant identification, onset date, will include the following information: treatment, participant identification, country, age, gender, race, BMI, primary SOC, PT, reported term, onset date, study day (relative day to the start date of IMP), AE duration, duration of exposure, intensity, corrective treatment, action taken with IMP, date of treatment discontinuation (if relevant), relationship to IMP/NIMP/study procedures, outcome, date of death if any, seriousness, seriousness criteria, and AE status.

Similar to AE listing, listing for all adjudicated AEs will be provided plus adjudication outcome.

#### **2.3.5.2 Deaths**

The following summaries of deaths will be generated for the safety population.

- Number (%) of patients who died by study period (on-study, on-treatment, post-study)
- Deaths in nonrandomized patients or randomized but not treated patients
- Primary cause of death as adjudicated by CEC (by 3 major categories of causes [i.e., cardiovascular, non-cardiovascular, and undetermined], and by additional subcategories per CEC charter).
- Primary cause of death as reported by the investigator.

- Treatment-emergent adverse events leading to death (death as an outcome on the adverse event case report form as reported by the Investigator) by primary SOC and PT showing number (%) of patients sorted by internationally agreed SOC order, with PT presented in alphabetical order within each SOC.
- TEAEs leading to death (death as an outcome on the adverse event case report form page as reported by the Investigator) by primary SOC and PT
- Number (%) of patients with AEs leading to death by primary SOC and PT during the on-study period

### **2.3.5.3 Analyses of laboratory variables**

This section will be organized by biological function as specified in [Section 2.1.4.3](#).

The summary statistics (including number, mean, median, standard deviation, minimum and maximum) of all protocol-required laboratory variables (central laboratory values, changes from baseline and/or percent change from baseline [e.g., lipid parameters, albumin, total protein, hemoglobin, hematocrit]) will be calculated for each visit or study assessment (baseline, each post-baseline time point, last on-treatment value) by treatment group. For selected laboratory parameters (eg, ALT, AST, and ALP), descriptive statistics will also be summarized by upper limit of normal (ULN) values. Graphical presentations will be used to examine trends over time using mean ( $\pm$ SE) and/or mean change from baseline ( $\pm$ SE) at scheduled visits. Results will be presented in standard international unit.

The incidence of PCSAs (list provided in [Appendix A](#)) at any time during the treatment-emergent adverse event period will be summarized by biological function and treatment group whatever the baseline level and/or according to the following baseline status categories:

- Normal/missing
- Abnormal according to PCSA criterion or criteria

For parameters for which no PCSA criteria are defined, similar table(s) using the normal range will be provided as necessary. For calcitonin, no PCSA criterion is defined. Similar summaries will be provided using the pre-defined categories:  $\leq$ ULN,  $>$ ULN - 20 ng/L,  $\geq$ 20 -  $<$ 50 ng/L, and  $\geq$ 50 ng/L (Note that ng/L is the standard international unit and is equivalent to pg/mL).

All measurements collected during the On-treatment period, including values from unscheduled visits, will be considered for the PCSA summaries. However, when several measurements are performed on the same date and at the same time for a given laboratory test, the central laboratory value will be selected over the local lab value. These summaries will include patients in the safety population who have at least 1 assessment performed during the On-treatment period. When a PCSA definition involves a change from baseline value, patients must also have a baseline value to be included in the summaries, and when required by the definition of the abnormality, patients must also have available laboratory normal ranges.

For some parameters, such as liver enzymes, the lower limit of normal (LLN) is not considered clinically relevant, and values below this limit are considered normal. When there are multiple PCSA criteria for a specific parameter (eg, ALT), the participant will be counted once during the On-treatment period for the specific parameter in question under the worst/maximum PCSA category.

Elevation of liver parameters will be summarized by treatment group in safety population.

For PCSA, both central and local lab data will be used, though centralized data will be used preferentially to the local measures in the analysis when several measurements are performed on the same date and at the same time for a given laboratory test.

A listing of patients with at least 1 on-treatment PCSA (or out of normal range when no PCSA criteria is defined) will be provided (except for mild and moderate eGFR decreases) and will display the entire patients' profile across time for all parameters belonging to the corresponding biological function. Individual data listings will include flags when applicable:

- Baseline values will be flagged “B”.
- Normal laboratory ranges, available for most laboratory parameters, will be identified as ULN and LLN. Baseline, last on-treatment value, and individual data will be flagged “L” if the value is below the LLN and will be flagged “H” if it is above the ULN.
- Laboratory PCSA criteria will be used for the corresponding laboratory parameters. Values reaching a PCSA limit will be flagged (+, ++, -, or -- depending upon the direction and level of the abnormality). Flags for WBC and differential counts will be determined using data expressed in international units.

For parameters whose PCSA criteria are multiples of the ULN, the parameter's value will also be expressed as a multiple of the ULN in the individual data provided.

#### **2.4.4.1 Analyses of vital sign variables**

The summary statistics (including number, mean, median, standard deviation, minimum and maximum) of all vital sign variables (values and change from baseline) will be calculated for each scheduled visit (baseline, each post-baseline time point, last on-treatment value) by treatment group.

The incidence of PCSAs at any time during the On-treatment period will be summarized by treatment group irrespective of the baseline level and/or according to the following baseline status categories:

- Normal/missing
- Abnormal according to PCSA criterion or criteria

A listing of patients with at least 1 post-baseline PCSA will be provided and will display the patient's profile over time of all vital sign parameters. Individual data listings will include the following flags:

- Baseline values will be flagged "B",
- Parameter values reaching a PCSA limit will be flagged ('+' or '-' depending on the direction).

#### **2.4.4.2 Analyses of electrocardiogram variables**

The frequency and percentage of 12-lead ECG interpretation (normal, abnormal) will be provided at each scheduled visit by treatment group.

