8.2.3 Electrocardiograms

- The 12-lead ECG should be performed after at least 10 minutes in supine position and prior to other study procedures at that visit (eg, blood collection, IMP administration, etc). The Investigator should review the ECG and document the interpretation, sign and date it on the ECG print out and report it in the e-CRF. Each ECG trace is analyzed in comparison with the Screening ECG. All original ECG traces are kept as source data. The ECG assessment of "normal" or "abnormal" will be analyzed.

Note: Any new ECG abnormality should be rechecked for confirmation and reported as an AE if considered clinically significant by the Investigator.

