Vital signs and laboratory data	Adverse event incidence table for all types of TEAE will also be provided by treatment group in the subsets of participants on the background therapy of metformin + SGLT2, and on metformin + sulfonylurea.
ECG	For quantitative safety parameters based on central laboratory/reading measurements, descriptive statistics will be used to summarize results and change from Baseline values by visit and treatment group.
	The incidence of potentially clinically significant abnormalities (PCSA), defined as abnormal values

Endpoint	Statistical Analysis Methods
	considered medically important by the Sponsor according to predefined criteria/thresholds based on literature review, will be summarized at any time during the on-treatment period. Results will be presented both in standard international and conventional US units The incidence of Normal and Abnormal ECG status at any time during the on-treatment period will be summarized by treatment group whatever the Baseline level and according to Baseline status.
Exploratory	Will be described in the statistical analysis plan finalized before DB lock

HLGT: higher-level grouped term; HLT higher-level term; LLT: lower-level term; PT preferred term; SOC: system organ class; TEAE treatment-emergent adverse event

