### **2.1.4.2 *Electrocardiogram variables***

12-lead ECGs performed locally at the Investigator site. ECG assessments will be described as normal or abnormal.

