#### **2.5.5 Unscheduled visits**

Unscheduled visit measurements of laboratory data, vital signs, and ECG will not be included in the by-visit summaries, but will be used for computation of baseline, last on-treatment value, and PCSAs.

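### The SAP plans only by-visit normal/abnormal ECG percentages and omits, without declaring it, the protocol's any-time on-treatment ECG incidence by baseline status

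*SAP*

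**What the plan says.** Table 8 in Protocol 9.4.2 describes the ECG analysis: "The incidence of Normal and Abnormal ECG status at any time during the on-treatment period will be summarized by treatment group", and this is to be done "whatever the Baseline level and according to Baseline status". It therefore asks for two things, a count over the whole on-treatment period and a split by the baseline reading.

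SAP 2.4.4.2 gives the ECG analysis in a single sentence: the frequency and percentage of each reading ("normal, abnormal) will be provided at each scheduled visit by treatment group"). It mentions no any-time count, no cross-classification by baseline, no last on-treatment value and no table of potentially clinically significant abnormalities (PCSAs).

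Two other SAP rules bear on the point. Section 2.1.4.2 defines the variable: "ECG assessments will be described as normal or abnormal". Section 2.5.5 deals with extra readings: "Unscheduled visit measurements of laboratory data, vital signs, and ECG will not be included in the by-visit summaries". The same rule lets them count towards the baseline value, the last value on treatment and the PCSAs.

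On data capture, Protocol 8.2.3 asks the investigator to "document the interpretation, sign and date it on the ECG print out and report it in the e-CRF". It also requires any new abnormality to be rechecked, and to be reported as an AE if the investigator judges it clinically significant.

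**The concern.** The 12-lead ECG is listed among the endpoints of the secondary safety objective. A participant can qualify through a prior myocardial infarction or multivessel coronary disease, so it is foreseeable that some baseline ECGs will already be abnormal, although the documents give no rate. In such a population, the useful safety question is how many participants with a normal ECG at baseline had an abnormal one on treatment, in each arm. The protocol's table answers it directly. The SAP's table does not, and the SAP does not say that the analysis was changed.

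The stake is the quality of a descriptive safety summary. No hypothesis test depends on it.

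**Working it through.** The documents give no ECG figures, so there is nothing to reproduce. The check sets the texts side by side, followed by one illustration on assumed percentages.

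**1. The two analyses compared**

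| | Protocol 9.4.2, Table 8 | SAP 2.4.4.2 |
|---|---|---|
| Time frame | Any time on treatment | Each scheduled visit |
| Counting | Each participant once over the period | Each reading in its visit column |
| Baseline | Overall and split by baseline status | Week 0 is a column; no cross-classification |
| Unscheduled ECGs | Neither named nor excluded | Excluded by SAP 2.5.5 |

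**2. Is the change declared?** No. SAP 1.6 reads as not applicable. The list of statistical changes in SAP 1.5 has no ECG entry, and the safety table in Appendix B has no ECG row. The laboratory section (2.3.5.3) and the vital signs section (2.4.4.1) both keep an any-time on-treatment incidence with baseline-status categories. Only the ECG section lacks it, which looks more like an omission than a decision.

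**3. What by-visit percentages identify.** Take the same participants at Week 0 and Week 12. Let p0 and p1 be the proportions abnormal, n the proportion newly abnormal and r the proportion that reverted to normal. Then p1 = p0 + n − r, so n = (p1 − p0) + r. The rate among those normal at baseline is n / (1 − p0). The table gives p0 and p1 but not r. With assumed p0 = 0.30 and p1 = 0.32:

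| Reversion assumed | r | n = 0.02 + r | n / 0.70 |
|---|---|---|---|
| None | 0 | 0.02 | 2.9% |
| One in ten of those abnormal at baseline | 0.03 | 0.05 | 7.1% |
| One in three | 0.10 | 0.12 | 17.1% |
| All (upper bound) | 0.30 | 0.32 | 45.7% |

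The same two published percentages fit every row. The protocol's split by baseline status gives n / (1 − p0) directly.

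**4. Can the columns be added up to an any-time incidence?** No. The Schedule of Activities (Protocol 1.3) places ECGs at Week 0, Week 12, and then either at the premature end-of-treatment visit (for those who stop IMP early) or at closeout (for those who do not). The last two columns hold different participants. Anyone abnormal both at Week 12 and at the late visit would be counted twice in a sum.

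**5. Where do on-treatment unscheduled ECGs go?** The rechecks required by Protocol 8.2.3 will produce some. They are kept out of the by-visit tables and directed to baseline, last on-treatment value and PCSAs.
- Last on-treatment value: the general rules in SAP 2.3.5 set this up for quantitative parameters from central measurement. The ECG is a local normal/abnormal reading, and 2.4.4.2 asks for no such row.
- PCSAs: the general rules name ECG and count unscheduled evaluations. The ECG criteria in Appendix A, however, need numeric heart rate, PR, QRS or QT values. Neither document defines these as analysed ECG variables, and no ECG PCSA table is specified.

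So no ECG table specified in the SAP includes on-treatment unscheduled readings.

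**The case against.** The case for leaving the SAP alone is reasonable in several respects.

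- **The by-visit table shows baseline.** A reader might infer that it hides emergent change altogether. It does not. Week 0 is a scheduled ECG visit, so each arm's starting prevalence is visible. If no abnormal ECG reverts, the rise from Week 0 equals the proportion newly abnormal, and the arms can be compared on that. This stands: information is lost only to the extent that readings revert, and the upper bound above needs extreme reversion.
- **Abnormal ECGs between visits are not simply lost.** A reader might infer that they are. New abnormalities judged clinically significant become AEs and enter the treatment-emergent AE tables whatever the visit. Cardiovascular events that are positively adjudicated leave the AE tables but remain in the adjudicated-event data. What drops out is mainly unscheduled abnormal readings judged not clinically significant. This also stands.
- **The PCSA route may exist in practice.** The eCRF is not among the documents, and nothing in them rules out capture of ECG intervals. If intervals were collected, the general PCSA rules could cover part of the gap. What remains is that no ECG PCSA table is specified.
- **Few ECGs are scheduled.** There are about two post-baseline ECGs per participant, so the any-time count adds mainly the rechecks and the linkage to baseline. This limits the size of the point, but the linkage to baseline is what the protocol asked for.
- **The Week 12 amendment is not defeated.** Its stated purpose is earlier assessment by investigators, and the SAP does tabulate Week 12.

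**Conclusion.** The discrepancy holds. The protocol commits to an any-time on-treatment ECG incidence, overall and by baseline status; the SAP replaces it with by-visit percentages and declares no change. The planned tables therefore show net change in prevalence, but not the rate of new abnormality among participants normal at baseline if some readings revert. They also give no any-time incidence, and no specified ECG table uses on-treatment unscheduled readings.

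The point is minor. It affects descriptive safety output only, with no bearing on the primary analysis, alpha or power. Patient-level data would still allow the table to be produced later. The numerical range rests on assumed prevalences and reversion rates and shows only that the margins do not determine the answer; it does not predict this trial's result. The statement about unscheduled ECGs rests on the variables that the two documents define.

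**What to change.** Add to SAP 2.4.4.2: the number and percentage of participants with an abnormal ECG at any time in the on-treatment period, including unscheduled ECGs, by treatment group, overall and by baseline status (normal, abnormal, and missing shown separately). The SAP's laboratory and vital signs tables pool missing with normal. Table 8 does not ask for that for ECG, and it could count a pre-existing abnormality as new. Table 8 does not name unscheduled ECGs either, so their inclusion should be written out. Keep the by-visit table.

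If the sponsor prefers by-visit output alone, the change should be declared and justified in SAP 1.6. In either case, the SAP should define the ECG parameters that the Appendix A criteria need, or remove ECG from the PCSA rules.

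The cost is one table from data already collected and a few lines of SAP text.
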